4 STUDY PLAN

4.1 Study Design

This study is a Phase 2, multicenter, international, double-blind, randomized, placebo-controlled, parallel-group trial to assess the efficacy and safety of VIB7734 in participants with moderate to severely active SLE.

[figure not shown]
In this study, approximately 195 participants will be randomized in a ratio of 1:1:1 (65 participants per group) to receive VIB7734 200 mg Q4W SC, VIB7734 200 mg every 12 weeks (Q12W) SC, with an additional 200 mg SC dose at Week 4, or placebo. To maintain blinding, participants randomized to the VIB7734 200 mg Q12W SC dosing regimen will receive SC placebo injections on dosing visits outside the Q12W schedule. Randomization will be stratified by SLE Disease Activity Index 2000 (SLEDAI-2K) total score at Screening (\geq 10 or < 10) and prednisone or equivalent oral GC (OGC) dose at Baseline (Day 1) (\geq 10 mg or < 10 mg).

The study will comprise a Screening period of approximately 4 weeks (Days -28 to -1), Randomization on Day 1, treatment and assessments through Week 48, and a Safety Follow-Up (SFU) period of 8 weeks (through Week 56). Under exceptional circumstances such as delayed laboratory results, drug washout, or the impact of COVID-19, the Screening period may be increased by 2 weeks, upon approval by the Medical Monitor. The study will be conducted on an outpatient basis. For all administrations, IP will be administered by site staff in the clinic and the participant will be observed for at least 60 minutes after the first and second doses. Participants who prematurely stop dosing prior to Week 44 will be followed through Week 56. Participants will not automatically be removed from the study if any administration of IP is missed.

A long-term extension (LTE) study for safety and efficacy may be offered as part of a separate protocol, to participants who complete the Week 48 visit. Participants who enter the LTE study directly after completion of the Week 48 visit will not complete the visits of the SFU period.

The study design is summarized in Figure 1.

Figure 1 Study Design

^{*}Two Week extension under exceptional consideration (delayed labs, drug wash out, COVID-19-related delays) with Medical Monitor approval.

COVID-19: coronavirus disease 2019; OGC: oral glucocorticoid; Q4W: every 4 weeks; Q12W: every 12 weeks; SC: subcutaneous(ly); SLE: systemic lupus erythematosus; SLEDAI-2K: SLE Disease Activity Index 2000; W: week.

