8.2 Documenting Adverse Events

Report initiation for all AEs and SAEs will begin from the time of signing ICF and continue up until the final study visit. All events will be followed to resolution or until they are considered as a non-clinically significant event.

AEs reported by the participant, spontaneously or in response to an open question from the study personnel, and AEs revealed by observation will be recorded during the study at the investigational site.

Clinically significant abnormalities in vital signs, body weight, physical examination, laboratory parameters, and ECGs will be recorded as separate AEs or SAEs if they are not considered as part of pre-existing medical conditions or have already been recorded due to other AEs or SAEs. Worsening or new manifestations of SLE (eg, those captured by SLEDAI-2K, BILAG 2004 Index, or CLASI) do not have to be reported as AEs, unless they meet the criteria for a SAE. All AEs meeting criteria must be reported immediately.

For each AE, the Investigator will evaluate and report the onset (date and time), resolution (date and time), severity, causality, action taken, serious outcome (if applicable), and whether it caused the participant to discontinue the study. The AE term should be reported in standard medical terminology when possible.

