9.5.5 Safety Analysis

AEs will be coded using the Medical Dictionary for Regulatory Activities by System Organ Class and Preferred Term. The number and percentage of participants reporting treatment-emergent AEs with onset on or after the start of the first administration of IP will be summarized for each treatment group by System Organ Class and Preferred Term, by severity, and by relationship to the IP. The number and percentage of participants reporting treatment-emergent SAEs and treatment-emergent AESIs will also be summarized.

Clinically significant abnormalities in laboratory parameters, vital signs, ECGs, and physical examinations will be recorded as AEs or SAEs. Laboratory assessments, vital signs, and ECGs, as well as their changes from Baseline at each visit will also be summarized descriptively.

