## 3.8 Safety Analysis

## **3.8.1** Adverse Events

In general, if an adverse event (AE) onset is on or after the first dose of IP administration, the AE will be considered as a treatment emergent AE (TEAE). Otherwise, the AE will be considered as a non-treatment emergent AE.

An overall summary table will be showing the number and percentage of participants with at least 1 event in any of the following categories: TEAE, treatment emergent serious AE (TESAE), TEAE with outcome of death, TEAE leading to discontinuation of IP, grade 3 or higher TEAE, serious and/or grade 3 or higher TEAE, IP related TEAE, IP related TESAE.

AEs will be coded using the most recent version of MedDRA. All TEAEs will be summarized overall and by MedDRA SOC and PT, by severity and by relationship to IP. Specific AEs will be counted once for each participant for calculating rates, but all events will be presented in subject listings. In addition, if the same AE occurs multiple times within a particular participant, the highest severity and level of causality will be reported.

The TEAEs, TESAEs, TEAEs resulting in death, TEAEs leading to discontinuation of IP, Grade 3 or higher TEAEs, IP related TEAEs, and IP related TESAEs will be summarized by SOC and PT. TESAEs will be summarized by SAE criteria as well. In addition, a summary of TEAEs sorted by frequency will be presented by PT.

An AE of special interest (AESI) is an AE of scientific and medical interest specific to understanding of the IP and may require close monitoring and collection of additional information by the Investigator. AESIs for this protocol include:

- Hypersensitivity reaction, including anaphylaxis
- Viral infection/reactivation
- Opportunistic infection
- Malignancy (except non-melanoma skin cancer)

Treatment emergent AESIs will be summarized by SOC and PT.

Listings will be provided for all TEAEs and non-treatment emergent AEs.

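### Treatment-emergent status rests on onset date alone, so a Screening AE that worsens after the first dose may be missing from the by-arm AE tables

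*SAP*

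**What the plan says.** SAP 3.8.1 sets the rule. "In general, if an adverse event (AE) onset is on or after the first dose of IP administration", the event is treatment-emergent. The next sentence closes the class: "Otherwise, the AE will be considered as a non-treatment emergent AE". Protocol 9.5.5 likewise limits its AE summaries to "treatment-emergent AEs with onset on or after the start of the first administration of IP".

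Collection starts earlier than that. Protocol 8.2 states: "Report initiation for all AEs and SAEs will begin from the time of signing ICF and continue up until the final study visit". Protocol 4.1 plans about 4 weeks of Screening and adds that, in exceptional circumstances, "the Screening period may be increased by 2 weeks, upon approval by the Medical Monitor".

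On the content of a record, Protocol 8.2 states: "For each AE, the Investigator will evaluate and report the onset (date and time), resolution (date and time), severity, causality". The fields it goes on to name do not include a date of worsening or a date of becoming serious.

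The AE tables planned in SAP 3.8.1 (overall, by class and term, severity, relationship, death, discontinuation of investigational product (IP), Grade 3 or higher, serious) are all restricted to TEAEs. The table of AEs of special interest (AESIs) is restricted to treatment-emergent AESIs. Non-treatment-emergent AEs are promised only in listings.

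**The concern.** The database will hold AEs that began between consent and first dose. Some may still be ongoing at dosing and get worse on treatment. A worsening on treatment is a safety observation made after exposure, and the reader of the by-arm tables expects to find it there. Under a rule that looks only at the first onset date, it is not.

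The tables at stake are those in which single events carry weight: deaths, serious events, Grade 3 or higher events and AESIs. Listings do show the events, but they give no rates by arm and no comparison with placebo.

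**Working it through.** No formula underlies the rule, so the check sets the texts side by side and follows one event through them.

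**1. Can such events exist?** Yes. AE recording starts at consent. The pre-dose window is 28 days, or 28 + 14 = 42 days with the exceptional extension. The exclusion criteria bar significant infection and acute illness at entry, but not every ongoing AE. Criterion 16, for instance, lets chronic nail infections through.

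**2. Apply the rule.**

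| Event | How recorded | Class under SAP 3.8.1 | In by-arm AE tables? |
|---|---|---|---|
| Starts after first dose | Onset post-dose | TEAE | Yes |
| Starts in Screening, Grade 2, never worsens | Onset pre-dose | Not a TEAE | No, as intended |
| Starts on Day -10, Grade 2; Grade 4, serious or fatal on Day 30 | One record, onset pre-dose | Not a TEAE | No, listing only |
| Same event | New record opened at worsening | TEAE | Yes |

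The third row is the gap. The fourth shows the condition on which it depends.

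**3. Does any supplied text put the event in the fourth row?**
- The SAP rule opens with a general qualifier, but no exception for worsening follows it.
- The SAP 3.8.1 sentence on reporting the highest severity concerns an AE that recurs in the same participant. It does not reclassify an event with pre-dose onset.
- Protocol 8.2 neither requires nor forbids a new record at worsening. Its limit on separate recording concerns abnormal vital signs, weight, examinations, laboratory values and ECGs, not the worsening of an AE.
- Protocol 6.3.3.3 makes medically significant changes from the Screening physical examination AEs. That could catch some cases, but only those visible on examination.
- Protocol 11.4.2 refers to eCRF completion guidelines, which are not among the documents supplied.

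So no supplied text settles it.

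**4. Follow an AESI.** Protocol 8.1 makes a viral infection an AESI only from Grade 3. A mild viral infection present in Screening that reaches Grade 3 on treatment first becomes an AESI after dosing, and Protocol 8.3 then requires its report within 24 hours. With its original onset date, it is absent from the treatment-emergent AESI table. The SAP's own AESI list carries no grade limit for viral infection, but that does not help: the event would then be an AESI from a pre-dose onset, and still not treatment-emergent.

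**5. Which summaries do not depend on the rule?** Laboratory shift and worst-grade tables (SAP 3.8.2), vital signs and ECG (SAP 3.8.3), and disposition with reasons for stopping treatment or study (SAP 3.4.1). One side effect follows. A participant who stops IP because of a worsened Screening AE would be counted as a treatment discontinuation in the disposition table, yet not in the table of TEAEs leading to discontinuation.

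**6. Direction and size.** The rule can only remove post-dose worsening from the TEAE tables, never add to it. The removal applies to every arm. If the drug provoked worsening, more would be removed from the active arms, and the difference from placebo would shrink. With the planned 65 per arm, one omitted participant changes an arm's proportion by 1/65 = 0.015, or about 1.5 percentage points. The documents give no rate of ongoing Screening AEs or of their worsening, so no expected count can be derived.

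**The case against.** The strongest reply is that the omission is conditional. If the eCRF guidelines tell sites to open a new record at worsening, the onset rule already captures the event. That stands, and the point is worded accordingly. It does not remove the gap, because the definition itself says nothing and the analysis should not rest on an unstated entry convention.

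A second reply is that few events qualify. This also stands in large part. Criteria 15, 16, 18 and 22 exclude unresolved zoster, CMV or EBV infection, clinically significant active infection, acute illness and COVID-19, and eligibility is rechecked on Day 1. An infection that begins a few days before dosing would often prevent randomization. Worsening lupus is not an AE unless serious (Protocol 8.2).

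Third, the trial is an exploratory phase 2 study with descriptive safety analysis, the events remain in listings, and an independent committee reviews safety data. True, but none of this supplies by-arm counts in the reported tables.

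Three stronger readings may tempt a reader, and the documents support none of them:
- That these events vanish from all safety summaries. Step 5 shows otherwise.
- That on-treatment viral reactivation would be missed. A reactivation that begins after dosing has a post-dose onset and is a TEAE under the present rule.
- That Protocol 8.2 fixes one onset and one severity per event. It names the fields but does not say this.

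**Conclusion.** The point holds in conditional form. Both documents define treatment emergence by onset alone, the SAP places everything else outside the class, and neither has a worsening clause. Unless worsening is entered as a new AE record, an AE that starts in Screening and becomes more severe, serious or fatal after the first dose is kept out of the by-arm AE and AESI tables and is seen only in listings.

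The number affected is probably small and cannot be estimated from the documents. Any error is an undercount. It matters most for rare outcomes, where one case in an arm of 65 is visible. Efficacy and sample size are not touched. The conclusion assumes that the eCRF guidelines do not already require a new record at worsening; if they do, the change merely makes the definition match practice.

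**What to change.** In SAP 3.8.1, define a TEAE as an AE with onset on or after the first dose of IP, or with onset before it that increases in severity, becomes serious or becomes fatal on or after it. Align Protocol 9.5.5. Apply the definition to every TEAE-based table: serious, fatal, Grade 3 or higher, leading to IP discontinuation, related, and AESI.

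In the eCRF guidelines, have sites either record the date of worsening or open a new record at worsening with its own onset date. Choose one method, so that an event is not counted twice. Without that date, the fields named in Protocol 8.2 would not show whether a high grade was reached before or after dosing.

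The cost is one sentence in each document, one data instruction and slightly higher TEAE counts.

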8.1 Definitions

- Adverse event (AE) An AE is any untoward medical occurrence associated with the use of an intervention in humans whether or not it is considered intervention-related.
- Serious adverse event (SAE) An event is considered "serious" if, in the view of either the Investigator or Sponsor, it results in any of the following outcomes:
 - Death
 - A life-threatening AE (An event is considered "life-threatening" if, in the view of either the Investigator or Sponsor, its occurrence places the participant or participant at immediate risk of death. It does not include an AE or suspected adverse reaction that, had it occurred in a more severe form, might have caused death.)
 - Inpatient hospitalization or prolongation of existing hospitalization
 - A persistent or significant incapacity or substantial disruption of the ability to conduct normal life functions
 - A congenital anomaly/birth defect
 - Important medical events that may not result in death, be life-threatening, or require hospitalization may be considered serious when, based upon appropriate medical judgment, they may jeopardize the participant or participant and may require medical or surgical intervention to prevent one of the outcomes listed in this definition. Examples of such medical events include allergic bronchospasm requiring intensive treatment in an emergency room or at home, blood dyscrasias or convulsions that do not result in inpatient hospitalization, or the development of drug dependency or drug abuse.
- Adverse reaction An adverse reaction is any AE caused by a drug.
- Adverse event of special interest (AESI) An AESI is an AE of scientific and medical
 interest specific to understanding of the IP and may require close monitoring and
 collection of additional information by the Investigator. An AESI may be serious or
 nonserious.

The rapid reporting of AESIs allows ongoing surveillance of these events in order to characterize and understand them in association with the use of this IP.

The following AESIs will be particularly monitored in this study:

- Hypersensitivity reaction, including anaphylaxis.
- Severe (Grade 3 or higher) viral infections/reactivations.

- Opportunistic infection listed in Appendix 3 (all cases).
- Malignancy (except non-melanoma skin cancer).

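### SAP 3.8.1 lists the viral AESI without a severity limit, whereas Protocol 8.1 restricts it to Grade 3 or higher, so milder viral events could be counted in AESI incidence

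*SAP*

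**What the plan says.** Protocol section 8.1 (Definitions) names four AESI categories. Two carry qualifiers. The viral category is "Severe (Grade 3 or higher) viral infections/reactivations". The opportunistic category is "Opportunistic infection listed in Appendix 3 (all cases"), so a listed infection counts whatever its grade. The other two are hypersensitivity (including anaphylaxis) and malignancy (other than non-melanoma skin cancer).

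SAP section 3.8.1 (Adverse Events) introduces its own list with "AESIs for this protocol include". It gives the same four categories, but the viral entry reads only "Viral infection/reactivation" and the opportunistic entry has no reference to Appendix 3. The hypersensitivity and malignancy entries agree with the protocol.

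On reporting, the same SAP section says "Treatment emergent AESIs will be summarized by SOC and PT". It does not say whether AESIs are taken from the site's AESI report, from a list of preferred terms or from medical review. Protocol section 9.5.5 plans the same outcome: "The number and percentage of participants reporting treatment-emergent SAEs and treatment-emergent AESIs will also be summarized".

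**The concern.** AESI incidence is an outcome measure of the safety objective in both documents (Protocol section 3.2; SAP Table 1). A named outcome should have one definition, and here the two current documents give different ones for the viral category. The statistical programmer works from the SAP, and the SAP's text is the wider of the two.

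The viral category matters for this product. Protocol section 2.1.4 lists viral infection and reactivation among the important potential risks, and section 2.2 describes the cells that the drug depletes as major producers of interferon alpha in response to viruses. A reader of the study report would take the AESI table as the place where the protocol's severe viral events are counted. If mild and moderate events are mixed in, the reported figure no longer means what the protocol says it means.

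**Working it through.** The plan states no figure to reproduce, and the point rests on no sample size, error rate or event rate. The check is a comparison of the two current texts. It does not depend on the protocol's summary of changes.

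**Step 1: the four categories side by side**

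| Category | Protocol 8.1 | SAP 3.8.1 | Result |
|---|---|---|---|
| Hypersensitivity | includes anaphylaxis | the same | agree |
| Viral | Grade 3 or higher | no grade limit | scope differs |
| Opportunistic | Appendix 3 infections, every case | no reference to a list | cross-reference missing; scope cannot be compared |
| Malignancy | excludes non-melanoma skin cancer | the same | agree |

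**Step 2: what the viral difference admits.** Severity is graded on the five-level CTCAE v5.0 scale (Protocol 8.2.2). The protocol's viral category takes Grades 3 to 5; the SAP's, read as printed, takes Grades 1 to 5. The SAP category therefore contains the whole of the protocol category plus the Grade 1 and 2 events. Not all of those extra events are wrongly included, because a viral infection that appears in Appendix 3 is an AESI at any grade through the opportunistic category. The excess is therefore:

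Grade 1–2 viral infections or reactivations that are not listed in Appendix 3 and do not qualify under another category.

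**Step 3: effect on the reported incidence.** For an arm of *n* participants, let *k* be the number who have at least one excess event and no AESI under the protocol. Then

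incidence (SAP list) = incidence (Protocol 8.1) + *k*/*n*.

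Since *k* cannot be negative, the viral discrepancy can only raise the figure. The documents give no viral event rate, so *k* cannot be estimated. For the unit of scale only, with the planned *n* = 65 per arm each such participant adds 1/65 = 0.0154, about 1.5 percentage points.

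**Step 4: does anything else in the plan settle which definition applies?** Protocol 8.3 has sites report AESIs to the sponsor on a dedicated form after randomization. Forms completed under Protocol 8.1 should follow the protocol's definition, but the SAP does not name them as its source. The SAP defers some details expressly to the statistical programming plan (visit windows in 3.1.2, selection of immunosuppressants in 3.6) but makes no such deferral for AESIs. The conflict therefore stands in the plan as written.

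**The case against.** The strongest reply is that the SAP's lead-in, "AESIs for this protocol include", points back to the protocol, where the set is exactly defined, and that sites will in any case flag AESIs under the protocol. On that route the summary would follow Protocol 8.1 and *k* would be at or near zero. This limits the claim to what could happen. It does not remove the conflict, because the SAP prints its own wider list and does not tell the programmer to use the site reports.

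It can also be said that little is lost. All treatment-emergent events are tabulated by severity, and "Grade 3 or higher TEAEs, IP related TEAEs, and IP related TESAEs will be summarized by SOC and PT". A reader could pick out the severe viral events from those tables. That is right, and it is why the consequence is small. Those tables would still not give a ready count of participants with protocol-defined AESIs.

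Four stronger readings are tempting, and the documents do not support them:

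- **The SAP drops the number and percentage planned in Protocol 9.5.5.** It does not. SAP 3.1 summarizes categorical data as counts and percentages of participants, and 3.8.1 counts each specific event once per participant. The overall table has no AESI row, but the protocol does not ask for one there.
- **The opportunistic category is also wider.** Only a missing cross-reference can be shown. The contents of Appendix 3 are not in the text available for review, so the scopes cannot be compared.
- **The inflation can be put at some number of participants.** That would need a viral event rate, and none is given.
- **The unstated source of AESIs is a defect in its own right.** Taken alone it is missing detail. It matters here because it leaves the two definitions unreconciled.

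**Conclusion.** The point holds for the viral category. The current SAP and the current protocol define that AESI differently, and the SAP's wording is wider by Grades 1 and 2. If AESIs are selected from the SAP's list, viral events that the protocol does not regard as AESIs will enter a named safety outcome. If they are selected from site reports made under Protocol 8.1, they mostly will not. The plan does not say which.

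The size of the excess is unknown and cannot be estimated from the documents. Its direction is known: over-inclusion of milder events, possible in any arm. No efficacy result, error rate or power figure is touched, the sites' 24-hour reporting follows the protocol, and no severe event is hidden. Confidence is high that the wording conflicts; whether the reported incidence would change depends on the selection route. The discrepancy is worth correcting because it is specific, affects a reported number and costs almost nothing to remove.

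**What to change.** In SAP 3.8.1, replace the viral and opportunistic bullets with the wording of Protocol 8.1: viral infections or reactivations of Grade 3 or higher, and opportunistic infections listed in Appendix 3, all cases. Add a sentence saying that the treatment-emergent AESI summary applies this definition using the recorded CTCAE grade. A listed Appendix 3 infection then counts at any grade, and other viral infections count only from Grade 3.

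If the sponsor also wants viral infections of every grade, which would be reasonable given the potential risks in Protocol 2.1.4, show them in a separately labelled table that is not called AESI.

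The cost is two bullets and one sentence in the SAP, and a grade condition in the AESI program if events are selected from the list. No new data are needed, because the investigator records severity for every adverse event (Protocol 8.2) on the CTCAE v5.0 scale (Protocol 8.2.2).

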Section 8.1 – Definitions - The following AESIs will be particularly monitored in this study: • Hypersensitivity reaction, including anaphylaxis. • Viral infection/reactivation. • Opportunistic infection. • Malignancy (except non-melanoma skin cancer).	Section 8.1 – Definitions - The following AESIs will be particularly monitored in this study: • Hypersensitivity reaction, including anaphylaxis. • Severe (Grade 3 or higher) viral infections/reactivations. • Opportunistic infection listed in Appendix 3 (all cases).	Updated to clarify that AESI for viral infection and reactivation only includes those that are Grade 3 or higher and all cases of opportunistic infections listed in Appendix 3

	Malignancy (except non-melanoma skin cancer).	(which includes herpes zoster).
All SAEs, AESIs, pregnancies, overdose, or misuse must be reported to the Sponsor's designated representative, ICON, within 24 hours of site staff awareness by submitting a SAE/AESI/Pregnancy/Overdose Report Form by email to: ICON Patient Safety Email: [contact] Alternatively, the Report Form can be submitted by fax to: ICON Patient Safety [contact]	8.3 – Events Requiring Immediate Reporting All SAEs, AESIs (only after Randomization), pregnancies, overdose, or misuse must be reported to the Sponsor within 24 hours of site staff awareness by submitting a SAE/AESI/Pregnancy/Overdose Report Form by email to: Sponsor (Horizon Therapeutics/Viela Bio) Email: Alternatively, the Report Form can be submitted by fax to: Sponsor (Horizon Therapeutics/Viela Bio) [contact]	Updated to clarify that AESIs only need to be immediately reported after Randomization and contact information for immediate reporting.
	*All other references to ICON Patient Safety or ICON have been updated to indicated Sponsor throughout protocol	

STATEMENT OF COMPLIANCE

The study will be conducted in compliance with this clinical study protocol, Good Clinical Practice (GCP) as outlined by International Council for Harmonisation (ICH) E6(R2), and all applicable local and national regulatory requirements. Enrollment at any clinical study site may not begin prior to that site receiving approval from the ethics committee of record for the protocol and all materials provided to potential participants.

Any amendments to the protocol or changes to the consent document will be approved before implementation of that amendment. Reconsent of previously enrolled participants may be necessary depending on the nature of the amendment.

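### SAP 3.8.1 drops two limits in Protocol 8.1's AESI definition, names no source for the AESI flag, and gives AESIs no row in the overall AE table

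*SAP*

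**What the plan says.** Protocol 8.1 defines four AESI categories, two of them with limits: "Severe (Grade 3 or higher) viral infections/reactivations", and "Opportunistic infection listed in Appendix 3 (all cases" (the closing bracket is cut off here). Hypersensitivity carries no limit, and malignancy excepts non-melanoma skin cancer.

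SAP 3.8.1 opens its list with "AESIs for this protocol include" and names the same four categories. The viral item reads "Viral infection/reactivation", with no grade, and the opportunistic item does not mention Appendix 3.

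On tabulation, the SAP says "Treatment emergent AESIs will be summarized by SOC and PT". For the top-level table it says "An overall summary table will be showing the number and percentage of participants with at least 1 event" and then names the rows. AESI is not one of them.

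Both documents make AESI incidence a safety outcome (Protocol 3.2; SAP 2.1, Table 1). Protocol 9.5.5 plans a summary of the number and percentage of participants with treatment-emergent SAEs and with treatment-emergent AESIs.

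**The concern.** The SAP is the document a programmer works from. Its list is presented as this protocol's AESIs, yet for two of the four categories it omits what makes an event qualify. It also does not say whether AESIs come from the site reports required by Protocol 8.3 or from applying the SAP list to all adverse events. Two careful programmers could therefore produce different AESI counts for the same endpoint, both with a defensible reading of the text.

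Separately, the SAP states no place where the single figure that Protocol 9.5.5 asks for will appear, namely participants with any treatment-emergent AESI.

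What is at stake is the meaning of a descriptive safety rate. No efficacy result, hypothesis test or data collection step depends on it.

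**Working it through.** The plan states no figure to reproduce here. The check compares the operative texts.

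**1. Definitions side by side**

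| Category | Protocol 8.1 | SAP 3.8.1 | Agree? |
|---|---|---|---|
| Hypersensitivity, including anaphylaxis | no limit | no limit | yes |
| Viral infection or reactivation | Grade 3 or higher | no grade limit | no |
| Opportunistic infection | on the Appendix 3 list, all cases | no reference to the list | no |
| Malignancy | non-melanoma skin cancer excepted | same exception | yes |

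Two of four differ. The comparison uses current text on both sides and does not depend on the amendment log. As context only, the protocol's Summary of Changes gives the reason for the present wording: "Updated to clarify that AESI for viral infection and reactivation only includes those that are Grade 3 or higher". The narrowing was therefore deliberate.

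**2. Which events the two readings treat differently**

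Compare the SAP list applied literally with AESIs as sites report them under Protocol 8.1.

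- Viral event, Grade 3 or higher: an AESI under both.
- Viral event, Grade 1 or 2, on the Appendix 3 list: an AESI under both, because listed infections count in all cases. The Summary of Changes places herpes zoster on that list, so low-grade zoster makes no difference.
- Viral event, Grade 1 or 2, not on the list: an AESI under the SAP list only.
- Infection judged opportunistic, not on the list, and not a Grade 3 or higher viral event: an AESI under the SAP list only.

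The gap consists of the last two groups. The Appendix 3 list is not visible in the text available for this review, so neither group can be enumerated.

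**3. Unit of effect**

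Input: 65 participants per arm (Protocol 9.3; SAP 2.3). Take a participant whose only AESI under the SAP list is an event from one of those last two groups. That participant raises the arm's AESI incidence over the protocol's by

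1/65 = 0.0154 = 1.54 percentage points.

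This is one divided by the planned arm size. It is not an estimate of the total, because the documents give no expected number of such participants.

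**4. Rows in the overall AE table**

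SAP 3.8.1 names: (1) any TEAE; (2) serious TEAE; (3) fatal TEAE; (4) TEAE leading to IP discontinuation; (5) TEAE of Grade 3 or higher; (6) TEAE that is serious, Grade 3 or higher, or both; (7) IP-related TEAE; (8) IP-related serious TEAE. That is eight rows, none for AESIs. Protocol 9.5.5 names SAEs and AESIs together. The SAP gives the first an overall row and the second none. It promises TEAEs an overall line as well as SOC and PT rows, but for AESIs it mentions only SOC and PT.

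**5. Whether the overall figure can be recovered from the SOC and PT rows**

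The counting rule is "Specific AEs will be counted once for each participant for calculating rates". It prevents double counting within a specific event, not across several. Someone with two AESIs under different terms appears in two PT rows, so adding rows does not in general give the number of participants with any AESI.

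**The case against.** The strongest reply is that the SAP list is shorthand. Its lead-in refers to this protocol, and the sentence before it follows the protocol's general AESI definition closely. AESIs are a collected item: they appear in the visit schedules and, after randomization, go to the sponsor within 24 hours on a dedicated form. The SAP supplies no term list or search for deriving AESIs afresh. On that reading the site-reported set is used and the two documents agree in number. This is plausible and may well be what happens. What remains is that the SAP does not say so, and the list it does print is not the protocol's.

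A second reply is that Protocol 2.1.4 names viral infection and reactivation as a potential risk without any grade, so the SAP's label is closer to the stated risk. That is true, but the endpoint is AESI incidence, and Protocol 8.1 defines AESIs.

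A third is that an any-AESI line at the top of the SOC and PT table would satisfy Protocol 9.5.5. It would, but the SAP does not state one.

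A reader might go further and infer that low-grade viral infections will mask a difference in severe ones. The documents do not support this. The number of such infections is unknown, and Grade 3 or higher TEAEs have their own SOC and PT table. A reader might also infer that the plan breaks a commitment to report each AESI category separately. The protocol makes no such commitment, so a by-category table is a matter of layout.

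**Conclusion.** The definitions in the current SAP and current protocol conflict for two of four AESI categories, and the SAP names no source that would settle which governs. Taken literally, the SAP list gives an AESI incidence over a wider set of events. Taken through site reports under Protocol 8.1, it gives the protocol's. The missing AESI row is a smaller gap against Protocol 9.5.5, which the SOC and PT table could fill in practice.

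The consequence is small and descriptive. Its total size cannot be derived. The 1.54-point unit assumes exactly 65 treated participants in an arm and a participant with no other AESI. Individual events remain in the TEAE tables and listings under either reading. Confidence is high in the wording difference and the absent row, and low in any numerical effect.

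**What to change.** In SAP 3.8.1:

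1. Replace the AESI list with the four Protocol 8.1 definitions, including "Severe (Grade 3 or higher) viral infections/reactivations" and the restriction of opportunistic infections to Appendix 3 (all cases). Alternatively, state that AESIs are those defined in Protocol 8.1 and reported by sites on that basis.
2. Add a treatment-emergent AESI row, n (%), to the overall summary table, with each participant counted once.

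The cost is SAP wording and one table row. AESI reports and CTCAE grades are already collected, so no new data are needed. If the present list was meant literally, Grade 1 or 2 viral infections outside Appendix 3 would leave the AESI table. They would still appear in the TEAE tables by SOC, PT and severity.

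Optional, and not the correction of an error: also summarize AESIs by category, counting each participant once per category and an event that meets two categories in both. Zoster of Grade 3 or higher would be such an event, being both a severe viral infection and, per the Summary of Changes, on the Appendix 3 list.
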